#### **5.7.2.2. Neutralized Antibodies to JNJ-77242113**

The incidence of neutralizing antibodies (NAbs) to JNJ-77242113 will be summarized for participants who are positive for antibodies to JNJ-77242113 and have samples evaluable for NAb to JNJ-77242113.

#### **5.7.2.3. Antibody vs Efficacy/PK**

To explore the relationship between antibodies to JNJ-77242113 status and plasma JNJ-77242113 concentrations, efficacy and safety, the following analysis may be performed as appropriate:

- Summary of clinical response (e.g., PASI75 and IGA 0/1) by antibody to JNJ-77242113 status
- Summary of plasma JNJ-77242113 concentrations by antibody to JNJ-77242113 status
- Plots of median (IQ) plasma JNJ-77242113 concentrations over time by antibody to JNJ-77242113 status

#### **5.7.3. Pharmacokinetic/Pharmacodynamic Relationships**

The relationship between plasma concentration of JNJ-77242113 and PD may be analyzed graphically. If any visual trend is observed, a suitable PK/PD model may be developed to describe the exposure-response relationship. In the latter case, the results of the PK/PD modeling analysis will be presented in a separate technical report.

#### **5.7.4. Biomarkers**

Planned biomarker analyses may be deferred if emerging study data show no likelihood of providing useful scientific information. Any biomarker samples received by the contract vendor or sponsor after the cutoff date will not be analyzed, and therefore, excluded from the biomarker analysis.

Change in biomarkers over time will be summarized by treatment group. Associations between baseline levels and changes from baseline in select markers and response to treatment will be explored. The analyses will aim to identify biomarker relevant to treatment. Results of biomarker analyses will be reported in separate technical reports.

### 5.7.5. Definition of Subgroups

To evaluate the consistency of the primary efficacy endpoint PASI75 response and IGA at Week 16, subgroup analyses may be performed when the number of participants in the subset permits. The subgroups for subgroup analysis may include, but are not limited to the following:

#### Demographic subgroups

| Subgroup          | Variant | Definition   |
|-------------------|---------|--|
| Region            | 1       | Define based on UN guidance as per the M49 standard 
 
• North America
 
• Europe
 
                                      |
| Sex               | 1       | 
 
• male
 
• female
 
   |
| Race              | 1       | 
 
• American Indian or Alaska Native
 
• Asian
 
• Black or African American
 
• White
 
• Other
 
 |
| Age Group         | 1       | 
 
• <45
 
• 45-64
 
• ≥65
 
   |
| BMI               | 1       | 
 
• <25 kg/m^2
 
• 25-<30 kg/m^2
 
• ≥30 kg/m^2
 
                            |
| Body Weight Group | 1       | 
 
• ≤90 kg
 
• >90 kg
 
  |

#### Baseline disease characteristics and psoriasis medication subgroups

| Subgroup                           | Variant | Definition  |
|------------------------------------|---------|---|
| Age at diagnosis (years)           | 1       | 
 
• < median
 
• ≥ median
 
 |
| Psoriasis disease duration (years) | 1       | 
 
• < median
 
• ≥ median
 
 |
| Baseline PASI                      | 1       | 
 
• <20
 
• ≥20
 
           |
| Baseline IGA                       | 1       | 
 
• < 4
 
• = 4
 
           |
| Baseline BSA                       | 1       | 
 
• < 20%
 
• ≥ 20%
 
       |
| Baseline DLQI                      |         | 
 
• <10
 
• ≥ 10
 
          |
| Psoriatic arthritis                |         | 
 
• Yes
 
• No
 
               |

| Subgroup   | Variant | Definition  |
|--|---------|---|
| Phototherapy (ultraviolet B light [UVB] or psoralen and ultraviolet A light therapy [PUVA])  | 1       | 
 
Never used
 
Ever used
 
 |
| Conventional non-biologic systemics (PUVA, MTX, cyclosporine, acitretin, or Azathioprine)  |         | 
 
Never used
 
Ever used
 
 |
| Novel non-biologic systemic (apremilast, deucravacitinib, tofacitinib, baricitinib)  |         | 
 
Never used
 
Ever used
 
 |
| Biologics (Etanercept, Infliximab, Adalimumab, Ustekinumab, Briakinumab, Secukinumab, Ixekizumab, Brodalumab, Guselkumab, Risankizumab, Tildrakizumab, Alefacept, Efalizumab, Certolizumab pegol)                          |         | 
 
Never used
 
Ever used
 
 |
| Systemic Therapy (conventional nonbiologic systemics, novel nonbiologic systemics, 1,25-vitamin D3 and analogues, phototherapy, biologics, systemic herbal treatments/traditional Taiwanese, Korean, or Chinese medicines) |         | 
 
Never used
 
Ever used
 
 |
| TNF $\alpha$ agents (adalimumab, certolizumab pegol, infliximab, etanercept)   |         | 
 
Never used
 
Ever used
 
 |
| IL-12/23 inhibitors (ustekinumab, briakinumab)   |         | 
 

 
                              |
| IL-23 inhibitors (guselkumab, risankizumab, tildrakizumab)   |         | 
 
Never used
 
Ever used
 
 |
| IL-17(R) inhibitors (secukinumab, ixekizumab, brodalumab)  |         | 
 
Never used
 
Ever used
 
 |

## 5.8. Interim Analyses

An internal independent interim analysis committee (IAC) will be established to review the interim data available at the time of the IA to formulate recommended decisions and/or actions in accordance with the objectives of the interim analyses. The IAC will consist of at least a clinician and a statistician (neither of whom are involved in study conduct), one of whom will chair the committee, and other members as required. The details will be provided in a separate IAC charter.

The IAC will review the unblinded efficacy data and provide recommendations about the next step of study conduct and the future development of the compound based upon the results of the interim efficacy analyses. The interim analysis will occur after approximately 67% of the participants who received at least one administration of study intervention have completed their Week 8 visit or have terminated their study participation before Week 8. The objective of the interim analysis is to determine whether the efficacy of JNJ-77242113, which is the proportion of participants achieving a PASI 75 response at Week 8, is sufficient to initiate the at-risk planning for the future development of JNJ-77242113 CCI for psoriasis based on the data accrued up to the interim

analysis. No changes to the current study are planned. Other selected supportive efficacy endpoints could also be reviewed. The unblinded results will be limited to specific sponsor personnel not involved in the study conduct. Interim analysis results will not be disseminated to investigators or individuals associated with the conduct of the study.

Details of the plan for the interim analyses will be specified in the Interim Analysis SAP.

#### **5.8.1. Data Monitoring Committee (DMC) or Other Review Board**

An external independent data monitoring committee (iDMC) whose members are not directly involved in the conduct of the study, will review unblinded safety data to ensure the safety of the participants enrolled in this study. The committee will meet regularly to review unblinded safety data. After the review, the iDMC will make recommendations to the sponsor regarding the conduct of the study. The iDMC will consist of at least one clinical physician and one statistician, not involved in the conduct of the study. The iDMC responsibilities, authorities, and procedures will be documented in the iDMC charter

An independent, external DMC has been established to monitor data on an ongoing basis to ensure the continuing safety of the participants enrolled in this study. The DMC consists of 3 members (including 1 dermatologist, one cardiologist and one statistician) who are independent of the sponsor. None of the members is participating as an investigator in the current study.

The major function of the DMC is to monitor the safety of the study agent by reviewing the serious adverse events (SAEs) each month and by reviewing the study safety data approximately every 4 months. The content of the safety summaries for this study are defined and documented in the DMC SAP developed by the sponsor. No hypothesis testing will be conducted. An independent statistical supporting group, provided by SGS, supports the DMC and is the liaison between sponsor and the DMC.

In addition, the DMC roles and responsibilities, and the general procedures (including communications) are defined and documented in the Data Monitoring Plan developed by the sponsor detailing the safety data monitoring to be conducted by the DMC.

## 6. SUPPORTING DOCUMENTATION

### 6.1. Appendix 1 List of Abbreviations

|                   |  |
|-------------------|--|
| ADA               | anti-drug antibody   |
| AE                | adverse event  |
| ALT/SGPT          | alanine aminotransferase   |
| AST/SGOT          | aspartate aminotransferase   |
| ATC               | anatomic and therapeutic class   |
| AUC               | area under the curve   |
| BMI               | body mass index  |
| BSA               | body surface area  |
| CI                | confidence interval  |
| C max  | maximum concentration  |
| CRF               | case report form   |
| CSR               | Clinical Study Report  |
| CTCAE             | Common Terminology Criteria for Adverse Events   |
| CV                | coefficient of variation   |
| DMC               | Data Monitoring Committee  |
| DPS               | Data Presentation Specifications   |
| eCRF              | electronic case report form  |
| F (%)             | absolute SC bioavailability  |
| FAS               | full analysis set  |
| FDA               | Food and Drug Administration   |
| ICH               | International Conference on Harmonisation  |
| IQ                | interquartile  |
| IWRS              | interactive web response system  |
| LLOQ              | lower limit of quantification  |
| MedDRA            | Medical Dictionary for Regulatory Activities   |
| MMRM              | Mixed-Effect Model Repeated Measure  |
| MRD               | minimum required dilution  |
| NAb               | neutralizing antibodies  |
| PD                | pharmacodynamic(s)   |
| PI                | principal investigator   |
| PK                | pharmacokinetic(s)   |
| PP                | per protocol   |
| SAE               | serious adverse event  |
| SAP               | Statistical Analysis Plan  |
| SD                | standard deviation   |
| SMQs              | standardised MedDRA queries  |
| TEAE              | treatment-emergent adverse event   |
| T max  | time to maximum concentration  |
| US NCI            | United States National Cancer Institute  |
| V                 | volume distribution  |
| V z    | volume of distribution based on terminal phase   |
| V z /F | apparent volume of distribution based on terminal phase after extravascular administration |
| WHO               | World Health Organization  |
| WHO-DD            | World Health Organization Drug Dictionary  |

## **6.2. Appendix 2 Changes to Protocol-Planned Analyses**

N/A

### 6.3. Appendix 3 Demographics and Baseline Characteristics

The number of participants in each analysis set will be summarized and listed by intervention group, combined active intervention group, and overall. In addition, the distribution of participants by region, country, and site ID will be presented unless otherwise noted.

[Table 3: Demographic Variables](#) presents a list of the demographic variables that will be summarized by intervention group, combined active intervention group, and overall for the FAS analysis set.

**Table 3: Demographic Variables**

| Continuous Variables:  | Summary Type   |
|--|--|
| Age (years)  | Descriptive statistics (N, mean, standard deviation [SD], median and range [minimum and maximum], and IQ range). |
| Weight (kg)  |  |
| Height (cm)  |  |
| Body Mass Index (BMI) (kg/m  )   |  |
| Body Surface Area (BSA) (m  )  |  |
| Categorical Variables  |  |
| Age (<45 years, 45-64 years, and ≥65 years)  | Frequency distribution with the number and percentage of participants in each category.                          |
| Sex (male, female)   |  |
| Weight (<90 kg, ≥90 kg)  |  |
| Race (American Indian or Alaska Native, Asian, Black or African American, Native Hawaiian or other Pacific Islander, White, Unknown, Not Reported) |  |
| Ethnicity (Hispanic or Latino, not Hispanic or Latino)   |  |
| BMI ([normal <25 kg/m  , overweight 25-<30 kg/m  , obese ≥30 kg/m  ])  |  |

aIf multiple race categories are indicated, the Race is recorded as 'Multiple'

Baseline disease characteristics (e.g., duration of psoriasis disease, baseline Hurley stage status, baseline PASI score, baseline IGA score, baseline BSA, baseline PRO related measurements, and baseline reginal psoriasis related measurements) will be summarized by treatment group. In addition, summaries of participants' medical history and current diagnoses, alcohol intake, and smoking status will be provided by treatment group will also be provided.

#### **6.4. Appendix 4 Protocol Deviations**

In general, the following list of major protocol deviations may have the potential to impact participants' rights, safety or well-being, or the integrity and/or result of the clinical study. Participants with major protocol deviations will be identified prior to database lock and the participants with major protocol deviations will be summarized by category through Week 16 and through the end of study.

- Developed withdrawal criteria but not withdrawn
- Entered but did not satisfy criteria
- Received a disallowed concomitant treatment
- Received wrong treatment or incorrect dose
- Other

A listing of participants with major protocol deviations and a listing of patients who missed scheduled study agent administration will also be provided by randomized treatment group. In addition, analyses of COVID-19 related protocol deviations will be provided.

## 6.5. Appendix 5 Prior and Concomitant Medications

Prior medications are defined as any therapy used before the day of first dose (partial or complete) of study intervention. Previous psoriasis medications/therapy will be summarized by intervention group.

Concomitant medications will be coded using the World Health Organization Drug Dictionary (WHO-DD). Concomitant medications are defined as any therapy used on or after the same day as the first dose of study intervention, including those that started before and continue on after the first dose of study intervention.

Summaries of concomitant medications will be presented by anatomic and therapeutic class (ATC) term, and intervention group. The proportion of participants who receive each concomitant medication will be summarized as well as the proportion of participants who receive at least 1 concomitant medication.

Participants' psoriasis medication history with topical agents, phototherapy, non-biologic systemic therapies, and biologic medications will be summarized by treatment group for all randomized participants. If data are available, total cumulative duration of treatment with these medications will be summarized. In addition, reasons for which participants discontinued previous systemic therapies (contraindication, inadequate response, intolerance [ie, AEs], or other) will be summarized by randomized treatment group.

The number of participants who received concomitant treatment of moisturizer for psoriasis will be summarized by randomized treatment group.

Participants who received concomitant corticosteroids for indications other than psoriasis and/or psoriatic arthritis will be listed. Participants with concomitant prophylactic treatments for latent TB infection will also be listed.

**6.6. Appendix 6 Medical History**

Summaries of participants' medical history, general medical history, alcohol intake, and smoking status will be provided by treatment group. In addition, the distribution of participants by prior biologic use (yes/no) and type of biologic therapy will also be provided.

**6.7. Appendix 7 Intervention Compliance**

Treatment compliance will be assessed based through Week 16 on the full analysis set (FAS) for the study. Descriptive summaries (sample size, mean, standard deviation, median, and range) will be presented for the percent of compliance defined as the number of doses taken divided by the number of doses that should have been taken. Overall compliance will be categorized as  $> 100\%$ ,  $80 \text{ to } \leq 100\%$ ,  $60 \text{ to } < 80\%$ , and  $< 60\%$ . In addition, treatment compliance will be assessed by summarizing the protocol deviation of the study agent administration related to incorrect study agent or dose received and missed administrations.

**6.8. Appendix 8 Extent of Exposure**

The extent of exposure will be summarized for randomized participants that received at least one study agent administration. Distribution of participants through Week 16 by study agent lot will be analyzed. In addition, the number (%) of participants receiving the study drug during double blind treatment phase will be summarized by treatment group.

## **6.9. Appendix 8 Adverse Events of Special Interest**

Not Applicable.

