### **8.3.7. Adverse Events of Special Interest**

An adverse event of special interest (AESI; serious or non-serious) is one of scientific and medical concern specific to the sponsor's product or program, for which ongoing monitoring and expedited

communication (within 24 hours) by the investigator to the sponsor is warranted. The AESIs for JNJ-77242113 are active TB, malignancy, and potential Hy's Law cases.

A possible Hy's law case is defined by the occurrence of ALT/AST  $\geq 3 \times$  ULN, together with Tbili  $\geq 2 \times$  ULN or INR  $>1.5$  (if measured). Any possible Hy's Law case is considered an important medical event and should be reported to the sponsor in an expedited manner using the AESI form, even before all other possible causes of liver injury have been excluded ([FDA 2009](#)).

A confirmed Hy's law case must be reported as a SAE.

Any newly identified malignancy, case of active TB, or potential Hy's law case occurring after the first study intervention administration(s) must be reported by the investigator according to the procedures for SAE reporting in Section 10.4, Appendix 4; Adverse Events, Serious Adverse Events, Product Quality Complaints, and Other Safety Reporting: Definitions and Procedures for Recording, Evaluating, Follow-up, and Reporting. Investigators are also advised that active TB is considered a reportable disease in most countries. These events are to be considered serious only if they meet the definition of an SAE.

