#### **9.4.5. Safety Analyses**

Safety data, including but not limited to, AEs, SAEs, AESIs (active TB, malignancy, potential Hy's Law cases), discontinuation of study intervention due to AEs, changes in laboratory assessments, changes in vital signs, and changes in weight will be summarized. Intervention-emergent AEs will be summarized by treatment group and Medical Dictionary for Regulatory Activities (MedDRA) system organ class and preferred terms. Details will be specified in the SAP.

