### **5.6.2. Adverse Events**

The verbatim terms used in the CRF by investigators to identify adverse events will be coded using the Medical Dictionary for Regulatory Activities (MedDRA). Any AE occurring at or after the initial administration of study intervention is considered to be treatment emergent. If the event occurs on the day of the initial administration of study intervention, and either event time or time of administration are missing, then the event will be assumed to be treatment emergent. If the event date is recorded as partial or completely missing, then the event will be considered to be treatment emergent unless it is known to be prior to the first administration of study intervention based on partial onset date or resolution date. All reported treatment-emergent adverse events will be included in the analysis. For each adverse event, the number and percentage of participants who experience at least 1 occurrence of the given event will be summarized by intervention group.

Summary tables will be provided for treatment-emergent adverse events:

- AEs
- Serious AEs (SAEs)
- AEs leading to discontinuation of study intervention
- AEs of severe intensity
- AEs related to study intervention

In addition to the summary tables, listings will be provided for participants who:

- Had SAEs
- Had AEs leading to discontinuation of study intervention
- Had AEs of severe intensity
- Had AE for psoriasis

- Had suicidal ideation or suicidal behavior
- Had anaphylactic or serum sickness reactions

A listing of participants who died will be provided.

Since safety should be assessed relative to follow-up, most AE summary tables will include average weeks of follow-up for each intervention group.

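### The SAP marks AESIs as not applicable although the protocol defines three and says they will be summarised, so active TB and malignancy have no AESI-specific definition, table or listing

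*SAP*

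**What the plan says.** **Protocol.** Section 8.3.7 states: "The AESIs for JNJ-77242113 are active TB, malignancy, and potential Hy's Law cases". It asks for communication to the sponsor within 24 hours and makes clear that an AESI may be serious or non-serious. The synopsis places AESIs among the key safety assessments. Section 9.4.5 includes "AESIs (active TB, malignancy, potential Hy's Law cases), discontinuation of study intervention due to AEs" in its list of safety data to be summarised, and closes the paragraph with "Details will be specified in the SAP".

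**SAP.** The section meant to hold that detail, 6.9, is headed "Appendix 8 Adverse Events of Special Interest" and reads "Not Applicable". Section 5.6.2 says "Summary tables will be provided for treatment-emergent adverse events" and then names five tables: all AEs, serious AEs, AEs that end study treatment, severe AEs and related AEs. Its listings cover serious events, events that end treatment, severe events, psoriasis events, suicidality, anaphylactic or serum sickness reactions, and deaths. None is for AESIs, active TB or malignancy. Section 5.6.3.1 plans a summary of potential Hy's Law cases through Week 20. Appendix 2 of the SAP, which records changes to protocol-planned analyses, is marked N/A.

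**The concern.** The protocol hands the specification to the SAP, and the SAP says that there is nothing to specify. A programmer following the SAP would produce no AESI output, and nothing in the SAP shows that this was a decision.

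Protocol 2.3 describes this study and its companion Phase 2b study as the first in participants with psoriasis. The AESIs are the events that the sponsor itself singled out for close attention. Even a table of zeros by arm is a safety result if it was planned in advance. If events do occur, choosing which terms count as malignancy after unblinding is an avoidable weakness.

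**Working it through.** There is no arithmetic beyond a count. The check sets each protocol AESI against every SAP output that could show it.

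| AESI (protocol 8.3.7) | Identification rule in SAP | Dedicated SAP summary | Dedicated SAP listing | General AE tables (SAP 5.6.2) |
|---|---|---|---|---|
| Active TB | none | none | none | yes, by individual term |
| Malignancy | none | none | none | yes, by individual term |
| Potential Hy's Law case | yes (5.6.3.1) | yes (5.6.3.1) | none | only if reported as an AE |

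AESIs defined: 3. With a dedicated summary: 1. Without one: 3 − 1 = 2. With no SAP output of any kind: 0.

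**Why the last count is zero.** Protocol 8.3.7 concerns events after the first administration. SAP 5.6.2 treats any AE at or after first administration as treatment-emergent, includes all of them, and gives number and percentage per event by group. A TB or malignancy event recorded as an AE is therefore counted somewhere.

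**What the general outputs leave out.** Three cases show the limits.

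1. *Active TB or most malignancies on treatment.* Protocol 7.1 makes these reasons for discontinuing study treatment, so they would also enter the discontinuation table and listing.
2. *A basal cell skin cancer in a participant who stays on treatment.* Protocol 7.1 allows for this (up to two, adequately treated). If it is neither serious nor severe, it enters none of the 5.6.2 listings and is one line in the overall AE table.
3. *A non-serious, non-severe event found in follow-up, after treatment has ended.* It cannot be a cause of discontinuation, so it too is only a line in the AE table.

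Malignancy can also be coded to many different terms. The SAP gives no rule for collecting them, so no number of participants with any malignancy is produced per arm. Protocol 9.4.5 plans tables by system organ class, but neither document equates an organ class with this AESI.

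**Other places that might fill the gap.** The only TB-specific output in the SAP is the listing of prophylactic treatment for latent TB (Appendix 5), which is a different matter. SAP 5.8.1 refers to a separate DMC SAP, but that governs committee summaries and is not among the documents, so it cannot be credited.

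**Hy's Law wording.** The relevant sections differ on whether ALP must be below 2 × ULN:

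| Place | ALP condition |
|---|---|
| Protocol 8.3.1 (reporting) | yes |
| Protocol Appendix 6, monitoring text and footnote 2 | yes |
| Protocol Appendix 6, stopping-criteria table | no |
| Protocol 8.3.7 (AESI definition) | no |
| Protocol Appendix 2 (laboratory tests) | no, though it refers to 8.3.1 for reporting |
| SAP 5.6.3.1 | no |

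A participant with ALT or AST at least 3 × ULN, bilirubin at least 2 × ULN and ALP at least 2 × ULN is a case under 8.3.7 and the SAP, but not under 8.3.1.

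**The case against.** The best defence is that little is lost. Every treatment-emergent event is tabulated by arm, and the discontinuation rules in protocol 7.1 send most on-treatment TB and malignancy events into a second table and a listing. The SAP already plans a combined active column (5.6) and average weeks of follow-up (5.6.2). With a target of 80 participants, 16 weeks of treatment, and exclusions for active TB and recent malignancy, events may be few or none. Protocol 9.4.5 says that AESIs will be summarised but does not call for a dedicated table, and its own itemised AE analyses have no AESI entry.

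Most of this stands, and it limits the point. A reader might infer from SAP 6.9 that active TB and malignancy have no planned analysis at all. SAP 5.6.2 rules that out.

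A reader might also infer that the SAP's Hy's Law count depends on which definition a programmer picks. It does not: 5.6.3.1 gives one explicit rule, without an ALP condition, as in protocol 8.3.7. Having no ALP restriction, it also captures every case meeting the 8.3.1 thresholds. The ALP difference is a matter of consistency, chiefly within the protocol.

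The defence does not explain why the SAP calls AESIs not applicable when the protocol names three and defers to the SAP, or why SAP Appendix 2 is silent. Nor does it supply an identification rule, an aggregated malignancy count or a complete listing.

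**Conclusion.** The point holds in a limited form. SAP 6.9 contradicts protocol 8.3.7 and 9.4.5, and the departure is not declared. Two of the three AESIs lack any AESI-specific identification, grouping, table or listing. All three remain visible somewhere in the planned outputs, so this is a gap in specification and presentation, not a loss of safety data. It should be corrected before database lock because the SAP is wrong as written and the correction is small.

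The conclusion rests on the text of the two documents and on TB and malignancy events being recorded as AEs, as the protocol requires. It depends on no event rate; the documents give none for these events. The Hy's Law wording is a separate, smaller matter: the passages must be reconciled, and nothing here says which version is right.

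**What to change.** - **SAP 6.9:** replace the present entry with the three protocol AESIs and state how each is identified (the AESI form mentioned in protocol 8.3.7, a prespecified set of coded terms, or both; for Hy's Law, the laboratory rule). Correct the label as well, since 6.8 and 6.9 are both called Appendix 8.
- **SAP 5.6.2:** add one AESI summary (number and percentage of participants, with average weeks of follow-up) by arm and for the combined active group, and one participant listing. Cross-refer to the Hy's Law summary in 5.6.3.1.
- **If the sponsor prefers not to add these:** record the omission and the reason in SAP Appendix 2. That is the minimum.
- **Hy's Law wording:** reconcile protocol 8.3.1, 8.3.7, Appendix 2 and Appendix 6 with SAP 5.6.3.1 on the ALP condition, and use the agreed definition in the summary.

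The AESI changes cost one table, one listing and some SAP wording. The Hy's Law reconciliation is a wording change to the protocol and, if needed, to the SAP. The AESI additions change neither data collection, sample size nor study conduct.
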